## 2. BACKGROUND

### 2.1 Study Disease(s)

Breast cancer is the most frequently diagnosed cancer and the second cause of cancer death in American women [Jemal et al., 2011, Siegel et al., 2013]. Approximately, 15% of these cancers are classified as triple-negative breast cancer (TNBC), comprising those with absent expression of estrogen receptor (ER), progesterone receptor (PR) and human epidermal growth factor receptor 2 (HER2) [Foulkes *et al.*, 2010]. Together with human epidermal growth factor receptor 2 (HER2)-positive breast cancer subtype, triple negative breast cancer (TNBC) have the highest rates of brain metastases, with studies reporting up to 50% rate of CNS involvement among those subtypes [Lin *et al.*, 2008, Niwinska *et al.*, 2010, Lin *et al.*, 2012].

Initial treatment for patients with brain metastases typically includes surgery or radiotherapy, either whole brain radiotherapy (WBRT), stereotactic radiation, or both, depending of factors such as performance status, expected prognosis as well the localization and the number of CNS metastasis [Lim *et al.*, 2014]. In patients with limited metastases and good performance status, stereotactic radiation has emerged as a preferred definitive modality because it offers excellent local control, is associated with minimal acute and long-term toxicity, and does not significantly interfere with systemic therapy schedules [Lim *et al.*, 2014].

Even with improvement in local and systemic therapies, the prognosis of patients with breast cancer BM is poor, especially in TNBC [Kennecke *et al.*, 2010, Sperduto *et al.*, 2012]. A recent large retrospective study of 865 patients with BCBMs reported the median overall survival following the diagnosis of BCBMs of 7.3 months in patients with TNBC [Sperduto *et al.*, 2013]. Therefore, there is a great necessity of developing new therapeutic strategies for TNBC BMs.

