## 13. STATISTICAL CONSIDERATIONS

### 13.1 Study Design/Endpoints

This is an open-label, single arm phase II study to assess PFS in patients with TNBC and brain metastasis who will receive stereotactic radiation in combination with atezolizumab. The target enrollment is 45 participants.

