### 13.4 Interim Monitoring Plan

A safety run-in analysis will be performed after the first 6 patients are enrolled and have completed the assessment period for dose-limiting toxicity (DLT). The DLT assessment period encompasses the period from first dose of atezolizumab until Cycle 3 Day 1, to allow sufficient time from stereotactic radiation treatment to assess for DLT. If there are 3 or more dose-limiting toxicity (DLTs) in the first 6 patients included, the study will be closed to further enrollment. If this occurs, then any plans to re-open the study with a modified treatment plan will need to be formally reviewed and approved by the sponsor and by the DF/HCC SRC/IRB prior to activation. If there are less than 3 DLT within the first 6 patients enrolled, then the study will proceed to full accrual. All patients who receive at least one dose of study drug will be included in the efficacy analysis.

Table: Probability of continuing enrollment with  $\leq 2$  DLTs out of 6 subjects.

	Safety run-in using 6 subjects						
True DLT rate	0.1	0.2	0.3	0.4	0.5	0.6	0.7
Probability of continuing enrollment	98%	90%	74%	54%	34%	18%	7%

To assess for potential delayed radiation toxicities, a 6-month safety visit will be performed. Patients who stop protocol therapy before the 6 months post stereotactic radiation treatment visit will be evaluated by phone by a member of the study team. If at any point during the trial the risk of delayed radiation toxicity is deemed to be excessive, the trial will be terminated.

In addition to the safety run-in in the first 6 patients treated, a continual assessment of symptomatic necrosis at 6 months and at 1 year will be conducted, using the method of Ivanova, et al (25) that applies Pocock-style boundaries for the maximum-tolerated rates of toxicity. Specifically, rates of necrosis at 6 months that are 25% or greater or at 1 year that are 50% or greater are considered unacceptable. For each toxicity rule, the upper limit of the probability of early stopping,  $\phi$ , is set at 0.1 and the proportion with maximum-tolerated toxicity,  $\theta$ , is defined as half the unacceptable rate. The following gives the sequential stopping rules tabulated according to the number of events. For instance, if 3 events of symptomatic necrosis at 6 months are observed in the first 6 patients enrolled, or if 8 events are observed in the first 30 patients, the study would be terminated for excessive toxicity.

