### 13.6.2 Overall survival

Overall survival is defined as the time from first dose of atezolizumab (day 1 cycle 1) to death from any cause. Patients who are alive at the end of the study will be censored at the date of last known alive. OS will be analyzed using Kaplan–Meier product-limit estimates and will be plotted with two-sided 90% confidence bands using Greenwood’s formula for the variance. For evaluating median survival, a Brookmeyer-Crowley like test will be conducted using the one-sided  $\alpha = 0.05$ . Based on prior studies [Eichler *et al.*, 2008, Lin *et al.*, 2008, Nam *et al.*, 2008, Niwinska *et al.*, 2010, Anders *et al.*, 2011], the null hypothesis is that median overall survival is 5 months or less.

With a sample size of 45 defined by the primary endpoint of PFS, there will be 90% power to reject the null hypothesis if the true median OS is 10 months when patients are given stereotactic radiation in combination with atezolizumab. The Approximate Upper Critical Value to the hypothesis test is a median OS of 7.4 months, under the assumption of nonparametric exponential family of density function for the distribution of failure times. The following table shows the level of power if smaller levels of improvement in survival are true which may be clinically relevant.

Alternative Hypothesis: Median OS (HR versus null)	Power
10 months (HR = 0.5)	90%
8.33 months (HR = 0.6)	75%
8 months (HR = 0.625)	70%
7.5 months (HR = 0.667)	61%

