### Radiation Necrosis

Brain metastases treated with stereotactic radiation which enlarge post treatment will be evaluated for radiation necrosis by the treating radiation oncologist, via neuroradiology assessment, and/or through the use of dual-phase PET-CT studies (Horky *et al.*, 2011), as clinically indicated, according to standard of care. The cumulative incidence of necrosis will be evaluated as the time from first dose of atezolizumab (day 1 cycle 1) to detected necrosis. Patients without detected necrosis will be censored at the end of the study, whether due to death or other reason. Cumulative incidence will be analyzed using Kaplan–Meier product-limit estimates and will be plotted with two-sided 90% confidence bands using Greenwood’s formula for the variance.

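### The radiation-necrosis curve has Greenwood 90% bands with no interval scale and no zero-event rule, so zero events would be shown as 0% with zero width, and a plain-scale upper limit is too low too often

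*Combined protocol and SAP*

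**What the plan says.** Section 13.7, Radiation Necrosis, measures time from the first atezolizumab dose to detected necrosis and says of the curve: "product-limit estimates and will be plotted with two-sided 90% confidence bands using Greenwood" (the sentence goes on to Greenwood's formula for the variance). On follow-up it says: "Patients without detected necrosis will be censored at the end of the study, whether due to death or other reason". Sections 13.5 and 13.6.2 use the same interval wording for PFS and OS. None of the three names the scale on which the limits are formed. For necrosis there is no small-sample alternative and no rule for zero events.

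The documents give no expected necrosis rate. The only reference rates are in Section 13.4, for symptomatic necrosis: "rates of necrosis at 6 months that are 25% or greater or at 1 year that are 50% or greater are considered unacceptable", and the maximum tolerated rate "is defined as half the unacceptable rate", which makes it 12.5% at 6 months and 25% at 1 year. Section 13.1 sets the size: "The target enrollment is 45 participants".

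**The concern.** PFS and OS curves are expected to fall through 50%, where a Greenwood interval on any usual scale behaves reasonably. A necrosis curve for a tolerable treatment stays near zero, and two things go wrong there. Before the first event the Greenwood variance is exactly zero, so the display claims certainty when the data are least informative. After a few events, a symmetric interval around a small proportion puts the upper limit too low.

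The upper limit matters most for safety, because it shows how much necrosis the data still allow. Section 1.4.1 makes 6- and 12-month safety an objective, and Section 5.2.4.1.8 sets dedicated necrosis visits at those times.

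**Working it through.** The plan states no precision or coverage for this curve, so there is no figure of its own to reproduce.

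**Inputs.** n = 45 (Section 13.1). Two-sided 90%, so 5% per tail and z = 1.645 (Section 13.7). Deaths censored (Section 13.7). Median OS of 5 months (Section 13.6.2: "the null hypothesis is that median overall survival is 5 months or less"), 7.3 months (Section 2.1: "7.3 months in patients with TNBC") and 10 months (Section 13.6.2: "if the true median OS is 10 months"). Reference rates of 12.5% and 25% at 6 months (Section 13.4). Assumed here: constant necrosis and death hazards, and any true rate other than those reference rates.

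**Formulas.** With S the Kaplan-Meier estimate and G the Greenwood sum of d/[n(n-d)] over event times:
- plain upper limit: (1-S) + 1.645 × S × √G
- log-log upper limit: 1 - S^exp(1.645 × √G / |ln S|)
- exact upper limit for 0 of n: 1 - 0.05^(1/n)

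**Zero events.** G is an empty sum, so the band is 0 to 0% on any scale. The exact limit for 0 of 45 is 1 - 0.05^(1/45) = 6.4%. That assumes all 45 have known status. With an effective 20 it would be 1 - 0.05^(1/20) = 13.9%. Twenty is roughly the number alive at 6 months if median OS is 5 months: 45 × 0.5^(6/5) = 19.6.

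**One event in 45, no censoring.** S = 44/45 and G = 1/(45 × 44) = 0.000505, so √G = 0.0225. The plain upper limit is 0.0222 + 1.645 × 0.9778 × 0.0225 = 5.8%. On the log-log scale √G/|ln S| = 1.00 and exp(1.645) = 5.18, so the limit is 1 - 0.9778^5.18 = 11.0%. The exact limit is 10.1%.

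| Events in 45 | Plain upper | Log-log upper | Exact upper |
|---|---|---|---|
| 0 | 0% | 0% (degenerate) | 6.4% |
| 1 | 5.8% | 11.0% | 10.1% |
| 2 | 9.5% | 13.5% | 13.3% |
| 3 | 12.8% | 16.3% | 16.3% |
| 5 | 18.8% | 21.8% | 22.0% |

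**How often the 6-month upper limit lies below the true net risk (nominal 5%).** Simulated Kaplan-Meier curves, n = 45, deaths censored, across median OS of 5, 7.3 and 10 months:

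| True 6-month rate | Plain scale | Log-log scale | Source of rate |
|---|---|---|---|
| 25% | 8-9% | about 4% | Section 13.4, unacceptable |
| 12.5% | 12-14% | 2-4% | Section 13.4, maximum tolerated |
| 5% | 15-21% | 15-21% | assumed |
| 3% | 33-40% | 33-40% | assumed |

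At 3% and 5% the misses are all zero-event trials, so changing the scale does not help and only an exact limit does. Adding 24 months' accrual and 6 months' further follow-up (Section 13.2, stated there for PFS and OS) leaves the 6-month figures essentially unchanged.

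**At 12 months**, with that accrual and follow-up, the plain-scale miss is 10-16% at the tolerated 25%. The log-log scale is better but not perfect: 4-11% at assumed true 12-month rates of 10-12.5%.

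**The case against.** Four points on the other side have force.

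1. **The scale is open.** Greenwood's formula fixes the variance, not the scale, so a log-log interval already fits the text. This stands. It means the plain-scale error is a risk of the wording and not a certainty. It does not rescue the zero-event case.

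2. **No low rate is forecast.** A reader might infer that the plan's upper limit misses by up to about a third. The documents do not support that: such figures need a true rate near 3%, which appears nowhere, and they consist only of zero-event trials. The 12.5% rate is a tolerance and not a prediction.

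3. **The band decides nothing.** A reader might infer that it tests the 25% and 50% limits. Those limits are for symptomatic necrosis and are judged by the count boundaries in Section 13.4, whereas this curve covers all detected necrosis. Even if the band were used that way, without censoring the plain and exact limits disagree about excluding 25% at only one count: 7 of 45 (24.4% against 27.2%).

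4. **Net risk is not what patients experience.** A reader might infer that the display understates necrosis in general. The miss rates above are for net risk, as if nobody died. Because deaths are censored, one minus Kaplan-Meier overstates the proportion of patients who actually develop necrosis. With median OS 7.3 months, a net 12.5% at 6 months corresponds to an actual incidence of 9.6%; the same hazard gives 23.4% net and 14.3% actual at 12 months. Against actual incidence the plain upper limit misses only about 5-6% at 6 months and 2-3% at 12 months. Treating death as censoring is a separate issue, not covered here, but it rules out the general claim.

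**Conclusion.** The plan is wrong as written for the zero-event case. Followed literally, it reports 0% with a zero-width band where the exact upper limit is 6.4% with all 45 followed, and higher with fewer.

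Otherwise, naming the scale is a cheap improvement. If the plain scale is used, the upper limit for net risk is too low more than twice as often as nominal at the maximum tolerated 6-month rate (12-14% against 5%), and 8-9% of the time at 25%. The lower limit is not the problem: on the plain scale it misses less than 5% at these 6-month rates. The figures rest on constant hazards, median OS of 5-10 months and censored deaths; anything at lower true rates rests on an assumed rate.

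No trial decision changes. The consequence is confined to how an exploratory safety result is displayed and read.

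**What to change.** In Section 13.7, Radiation Necrosis, state that necrosis risk at 6 and 12 months will be given with pointwise two-sided 90% intervals on the complementary log-log scale, using the Greenwood variance. Add that when no events have been observed by a time point, an exact one-sided 95% upper limit will be reported with its denominator stated. This could be Clopper-Pearson or a beta-product limit that allows for censoring. If Clopper-Pearson is used, say how patients who die before the time point are counted.

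The PFS and OS wording in Sections 13.5 and 13.6.2 can stay. The cost is a sentence or two of analysis-plan text, with no change to design, sample size or data collection. The downside is a slightly less favourable reported upper limit.

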### Patient-reported outcomes

The PRO measure for this study will be the scores from the MDASI-BT assessment.

### Neurological examination

In order to standardize the evaluation of key neurological exam components, this study will use the Neurological Assessment in Neuro-Oncology (NANO) scale.

### Correlative endpoints

Previous studies demonstrated that, in addition to its direct cytoreductive effect, RT-induced cell death can be immunogenic, facilitating the recruitment and activation of antigen presenting cells (APCs) and priming of tumor antigen-specific T-cells[Shahabi *et al.*, 2015]. Recently, different groups demonstrated that RT to the tumor bed led to upregulation of PD-L1 on tumor cells, dendritic cells, and on myeloid-derived suppressive cells (MDSCs), which may contribute to impairment of T-cell function in the tumor[Liang *et al.*, 2013, Deng *et al.*, 2014, Sharabi *et al.*, 2014]. Furthermore, these groups also demonstrated that the combination of RT plus blockade of the PD-1/PD-L1 axis improved outcomes in different preclinical models compared with RT or anti-PD1/PD-L1 alone, including breast cancer models.

Recently, Herbst et al have demonstrated that patients who presented an increase of at least 5% in expression of PD-L1 in tumor microenvironment experienced a bigger likelihood to respond to treatment with the anti-PD-L1 Atezolizumab[Herbst *et al.*, 2014]. Also, modifications in molecular signature of tumor microenvironment also correlated with response rate to this drug. Because of this rationale, we plan to perform two research tumor biopsies: one at baseline and the other one just before the beginning of cycle 3 of atezolizumab. Biopsies will be performed in the case of accessible extracranial disease (which will be outside of the field of radiation).

With a sample size of 45 and assuming that there will be patients without accessible lesions, the table below indicates the power available to detect 20%, 30%, or 40% increases of PD-L1 positivity rate. The power calculation is based on McNemar's test with 1-sided alpha of 0.05 and assuming 2% of patients unexpectedly show PD-L1 positivity only in the baseline assessment,

Increase of PD-L1 positivity rate at C3D1	# of paired biopsies (baseline and at cycle 3)	Power
20%	20	64%
	30	79%
	40	88%
30%	20	85%
	30	95%
	40	98%
40%	20	96%
	30	99%
	40	99%

PD-L1 positivity seen at baseline and C3D1 samples will be summarized using contingency tables. An exploratory analysis is planned to evaluate PD-L1 change in continuous scale.

To explore the relationship between correlative endpoints obtained from cerebrospinal fluid (CSF) to genetic alterations detected in the tumor and plasma, patient and disease characteristics, and clinical outcomes, the following analyses are planned: cell-free DNA (cfDNA) from serial CSF samples will be quantified using ultra-low pass whole genome sequencing, evaluated as both a continuous factor, and using the pre-defined threshold of TFX > 10% as a dichotomous variable; whole exome sequencing (WES) will be performed to determine copy number and mutation calls.

For paired assessments of WES of tumoral DNA and CSF at baseline and at time of progression, concordance will be assessed as the proportion of overall agreement using bootstrapped standard error estimates and confidence intervals, and kappa statistics to assess non-zero agreement. The following table shows the true Cohen’s Kappa statistic there will be 80% power to detect given the prevalence of the phenotype, number of paired samples, and using a two-sided alpha = 0.05

Prevalence of	# of paired samples (tumor and CSF)	True Cohen’s kappa
20%	20	0.63
	30	0.53
	40	0.46
30%	20	0.61
	30	0.51
	40	0.44
40%	20	0.60
	30	0.50
	40	0.43

The association of baseline CSF assessments to PFS and OS will be explored using Kaplan-Meier estimation and Cox proportional hazard models, and the association to ORR and CBR will be assessed using logistic models. Serial assessments will be characterized using descriptive statistics, and the association to clinical outcome will be modeled as post-baseline time-varying covariates (PFS and OS) and longitudinal mixed effects models (ORR and CBR). All analyses will be exploratory and hypothesis generating and point estimates will be reported with 95% confidence intervals.

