## SCHEMA

TNBC – triple negative breast cancer; CNS – central nervous system; SRS – stereotactic radiation to brain metastasis;

- \*D1 of Atezolizumab (A) will be administered 2-7 days before the initiation of SRS.
- Bx1 – Baseline tumor biopsy will be obtained within 28 days of starting Atezolizumab.
- Bx2 – Reassessment biopsy will be obtained between C2D1-C2D21.
- Imaging will be performed at screening within 4 weeks before starting Atezolizumab. Tumor assessments, including brain magnetic resonance imaging and computed tomography of the chest, abdomen and pelvis, will be performed every 6 weeks ( $\pm 1$  week) for the first 24 weeks on treatment, and every 9 weeks ( $\pm 1$  week) thereafter, with additional scans as clinically indicated.
- **Blood samples will be collected within 7 days before starting treatment (baseline), at day 1 ( $\pm 3$  days) of cycle #3, #5, #9, and at progression or off protocol therapy, whichever comes first.**
- **Cerebrospinal fluid collection will be performed at 3 times points (baseline, before cycle 3, and at progression or off protocol therapy, whichever comes first).**

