### **1.5 Correlative Objectives**

- 1.5.1 To explore whether the number and/or type of mutations identified using a next generation sequencing (NGS) panel is correlated with patient outcomes (PFS, ORR, CBR, and OS).
- 1.5.2 To collect blood to study cell-free DNA for quantification of tumor DNA content and copy number variation, using ultra-low pass whole genome sequencing, and to explore whether cfDNA load is associated with patient outcomes (PFS, ORR, CBR, and OS).
- 1.5.3 To collect blood to study cell-free DNA for targeted sequencing and/or whole exome sequencing To compare mutations and copy number variation between cfDNA and tumor biopsies.
- 1.5.4 To characterize a broad array of immune markers in metastatic TNBC (characterization will be based on histology, protein expression, and mRNA expression), and their changes with immune checkpoint blockade.
- 1.5.5 To explore how different immunosuppressive and/or immune-stimulating immune marker profiles at baseline correlate with patient outcomes (PFS, CNS ORR, CBR and OS).
- 1.5.6 To characterize changes in immune marker profiles on treatment and at time of progression
- 1.5.7 To characterize serial changes in immune marker profile in peripheral blood mononuclear cells (PBMCs) and in plasma over the course of the trial treatment.
- 1.5.8 To explore whether induction of changes in the immunosuppressive and/or immune-stimulating immune marker profile in PBMC correlates with clinical outcomes (PFS, ORR, and OS).
- 1.5.9 To collect cerebrospinal fluid (CSF) to study cell-free DNA for quantification of tumor DNA content and copy number variation, using ultra-low pass whole genome sequencing, and to compare patterns of cfDNA serially over time in CSF compared to plasma.
- 1.5.10 To explore whether cfDNA load in CSF is associated with clinical outcomes (PFS, ORR, CBR, and OS).
- 1.5.11 To collect CSF to study cell-free DNA for targeted sequencing and/or whole exome sequencing before, on and after immunotherapy. To compare mutations and copy number variation between cfDNA in plasma versus CSF.

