## 9.4 Cerebrospinal fluid (CSF)

### 9.4.1 Collection

While CSF collection is optional, it will be encouraged. We plan to collect CSF for at least 10 patients at baseline for cytology and potential DNA isolation, before cycle 3 day 1, and at progression or off protocol therapy, whichever comes first. The samples will be banked in the DFCI breast tissue repository for these and future research purposes. These specimens will become the property of the DF/HCC.

The following CSF blood samples are optional\*:

Screening (baseline):

- 3-10 mL in sterile collection tubes

Cycle 2 Day 15 to day 21:

- 3-10 mL in sterile collection tubes

Off Treatment (at progression or off protocol therapy, whichever comes first):

- 3-10 mL in sterile collection tubes

\*Streck Cell-Free DNA BCT tubes may be used in place of sterile collection tubes. After collection, gently invert tube 10 times to ensure proper mixing of stabilization agent and store at room temperature until processing.

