- h. CT and/or MRI should be of the chest, abdomen and pelvis. Additional imaging studies (CT neck, plain films, etc.) are permitted as clinically indicated. The same radiographic procedures and technique must be used throughout the study for each patient. Assessments should be done during the last 15-21 days of a cycle, q6weeks for the first 24 weeks (i.e. C2, 4, 6, 8) and then can be reduced to q9 weeks (i.e. C11, 14, 17, etc.) until progression. For those taken off-study for reasons other than progressive disease, tumor measurements should continue to be repeated every 6-12 weeks until progression or beginning a new cancer therapy regimen. Failure to complete restaging after a patient has been taken off protocol therapy will not constitute a protocol violation.
- i. Hematology: hemoglobin, hematocrit, platelet count, RBC count, WBC count, percent and absolute differential count.
- j. Chemistry: sodium, potassium, chloride, bicarbonate, glucose, BUN, creatinine, calcium, total bilirubin, total protein, albumin, ALT, AST, alkaline phosphatase, and LDH.
- k. Beginning with cycle 4, TSH will be done every other cycle on Day 1 (i.e. cycles 4, 6, 8, etc.).
- l. In female subjects of child-bearing potential as defined in the eligibility criteria, serum or urine pregnancy test must be performed within **8 days** prior to initiating protocol therapy
- m. cfDNA is required to be drawn on C1D1, Day 1 of RT, C3D1, C5D1, C9D1, at each restaging visit, and at disease progression or discontinuation of protocol therapy, whichever comes first.
- n. Immune markers will be drawn on C1D1, Day 1 of RT, C3D1, C5D1, C9D1, and at disease progression or discontinuation of protocol treatment, whichever comes first.
- o. Baseline tumor biopsy should be obtained within 28 days of the first dose of Atezolizumab. The C2D1 biopsy should be performed as close to C2D1 as possible but may be collected between C2D1 and C2D21. Both the baseline and C2 biopsy are required for participants with accessible disease outside of the field of radiotherapy. A biopsy at the time of disease progression is optional for subjects who have accessible disease and have achieved an objective response (CR or PR) and/or experienced prolonged stable disease for ≥ 24 weeks.
- p. CSF collection will be performed at baseline, C2 day 15 to day 21, and at disease progression or discontinuation of protocol therapy, whichever comes first (±3 days) in at least 10 participants.

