#### 11.2.5 Clinical Benefit rate

Clinical benefit rate: defined as CR, PR and stable disease (SD)  $\geq$  24 weeks.

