#### Primary endpoint

The primary endpoint is PFS defined as time from first dose of atezolizumab (day 1 cycle 1) to progression or death due to any cause. Progression will be defined according to the bi-compartmental model proposed in the RANO-BM publication and is defined as the first detection of radiologic progression of intracranial (per RANO-BM criteria; Section 11.1), extracranial (per RECIST 1.1 criteria; Section 11.2), or both or unequivocal progression of non-measurable disease in the opinion of the treating physician (an explanation must be provided); with each compartment (CNS and non-CNS) assessed separately.

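### The serial CSF models in Section 13.7 do not set aside the sample triggered by progression or stopping therapy, so a cfDNA rise at progression can appear as an association with clinical benefit and, less strongly, with response

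*Combined protocol and SAP*

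**What the plan says.** The Schema fixes the CSF schedule: "Cerebrospinal fluid collection will be performed at 3 times points (baseline, before cycle 3, and at progression or off protocol therapy, whichever comes first". Table 9-1 and Section 9.4.1 agree and place the middle sample at cycle 2 day 15 to 21. Footnote p of the study calendar in Section 10 gives the trigger, window and number for the last one: "at disease progression or discontinuation of protocol therapy, whichever comes first (±3 days) in at least 10 participants". Collection is optional under Section 9.4.1. Each patient therefore has at most two post-baseline values, and one is drawn because an outcome occurred or treatment stopped.

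The objective in Section 1.5.10 is "To explore whether cfDNA load in CSF is associated with clinical outcomes (PFS, ORR, CBR, and OS". Section 13.7 analyses baseline CSF with Cox and logistic models. For the serial samples, "the association to clinical outcome will be modeled as post-baseline time-varying covariates (PFS and OS) and longitudinal mixed effects models (ORR and CBR". It does not leave out the progression/off-therapy sample, limit the models to values dated before the event, set a landmark, or name the time scale of the mixed models. It labels all these analyses exploratory and hypothesis generating, with 95% confidence intervals.

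PFS in Section 13.1 is the "time from first dose of atezolizumab (day 1 cycle 1) to progression or death due to any cause". Clinical benefit in Section 11.2.5 counts stable disease only when it lasts at least 24 weeks.

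**The concern.** Progression ends PFS and also triggers the last CSF sample. It largely decides CBR too: a patient without an objective response misses clinical benefit by progressing before 24 weeks, so such patients give the last sample early and patients with benefit mostly give it late. A mixed model with calendar time takes sampling times as unrelated to outcome. If cfDNA rises by a similar amount in everyone at progression, that rise is spread over fewer weeks in the no-benefit group and shows up as a steeper slope.

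At stake is the meaning of a positive finding under Section 1.5.10. A 95% interval that excludes no effect could be read as CSF cfDNA carrying information about benefit, when it reflects only that patients who progressed were sampled at progression.

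**Working it through.** Section 13.7 gives no sample size, power or error rate for the serial CSF models, so there is no stated figure to reproduce. Its kappa table concerns tumor-CSF agreement and does not bear on this.

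**Inputs from the documents.** Three CSF times, at least 10 patients and a window of ±3 days (Schema, Sections 9.4.1 and 10). Scans every 6 weeks to week 24, then every 9 (Section 10). Median PFS of 2 months under the null and 3.5 under the alternative (Section 13.2). CBR threshold of 24 weeks (Section 11.2.5).

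**Assumed.** Exponential PFS. Baseline and cycle 2 values equal to a patient level plus noise, unrelated to outcome. A shift of 0, 0.5 or 1 SD in the sample drawn at progression. The documents give no figure for this shift.

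**Step 1: timing.** P(PFS ≤ t) = 1 − 2^(−t/median). Six weeks is 6/(52/12) = 1.385 months:
- median 3.5: 1 − 2^(−1.385/3.5) = 0.24
- median 2: 1 − 2^(−1.385/2) = 0.38

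Twenty-four weeks is 5.54 months, so the share progression-free then is 2^(−5.54/3.5) = 0.33 or 2^(−5.54/2) = 0.15.

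**Step 2: mechanism.** Take two patients with no early change and the same 1 SD rise at progression, one progressing at the week 12 scan and one at week 33 (24 + 9). From baseline to last sample the slopes are 1/12 = 0.083 and 1/33 = 0.030 SD per week, a difference of 0.053 created by the dates alone. With time coded as baseline, cycle 2 and off therapy, the group contrast at the last visit is 1 − 1 = 0.

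**Step 3: CBR, mixed model.** The model has a patient intercept, CBR group, calendar time and their interaction, at two-sided 5%, with a 3.5-month median and the protocol's scan schedule.

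| CSF patients | Rise 0.5 SD | Rise 1 SD | Last sample left out |
|---|---|---|---|
| 10 | about 11% | 23% | about 5% |
| 20 | about 22% | 51% | about 5% |

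With visit-coded time the rate is about 6-9%.

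A second simulation tested group and interaction jointly and gave 15% of patients a possible early off-therapy date without progression. With a 1 SD rise it found 20% against 12% without the last sample at n=10, 33% against 7% at n=20, and 64% against 5% at n=40. With 0.5 SD it found 12% against 12.5% at n=10 and 16% against 10.5% at n=20. With no rise it already gave 9% at n=10 and n=20, so its small-sample rates should be compared with that level and not with 5%. A simple comparison of post-baseline group means showed only 6-9%. About 45% of post-baseline samples were drawn at progression.

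**Step 4: ORR.** With a 1 SD rise and responders assumed to progress somewhat later, the second simulation gave 13% against 8% at n=20 and 16% against 7% at n=40. If responders are assumed to progress much later (18 weeks plus a mean of 24, against 6 plus a mean of 6), the n=20 rate is 64%. The size depends on that assumption.

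**Step 5: PFS, time-varying Cox model, 1 SD rise.** If the progression sample is applied to the progression event, the rates are 31%, 75% and 98% at n=10, 20 and 40. With only values dated before the event they are 1-3%.

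**The case against.** The plan names no time scale and no interaction term, so the mixed-model inflation belongs to one plausible coding and not to the plan as written. That stands: visit-coded time nearly removes it. But the plan does not require visit coding, and calendar time is a natural choice when the last visit varies by months.

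A reader might infer that the PFS model will also reject falsely as a matter of course. The documents do not support that. Progression is normally known only once a scan shows it, so a sample triggered by it usually follows the scan. Section 5.5 allows treatment beyond RANO-BM/RECIST progression, and Sections 11.1.1.5 and 11.4.2 date confirmed progression back to the first worsening scan; both tend to put the sample after the PFS event. Ordinary counting-process coding then drops it. A gap remains: the ±3-day window permits earlier samples, a patient stopping for symptomatic deterioration may give the sample before the documenting scan, and Section 13.7 states no rule.

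A reader might also assume that every progressing patient shows a CSF rise. PFS covers both compartments, and the documents give no reason to expect a CSF rise when first progression is only extracranial. Not every last sample is drawn at progression either, since some patients stop for other reasons.

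Finally, Section 1.5.10 asks about association, not prediction, and a rise at progression is useful in itself given the interest in Section 2.6 in following tumor burden. That is a reason to report the last sample in its own right. It does not support pooling that sample into models of CBR or ORR. The baseline models in Section 13.7 are unaffected.

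**Conclusion.** The point holds in a limited form. As written, Section 13.7 allows the outcome-triggered sample into models of the outcome. For CBR with calendar time, false-positive rates are about 11-23% at n=10 and 22-51% at n=20 for a 0.5 to 1 SD rise, against about 5% without that sample. The second simulation shows smaller inflation, and none visible at n=10 with a 0.5 SD rise. For ORR the effect is weaker and rests on how much later responders progress. For PFS it is conditional on coding that the plan neither prescribes nor excludes. OS is not affected in this way, because the sample precedes death.

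These sizes rest on an assumed rise at progression, exponential PFS and uninformative early samples. It would go too far to say that the serial CSF analyses must give false findings, or that the trial's efficacy conclusion is at risk. They are exploratory, in perhaps 10 patients, with no decision rule. This is a cheap improvement.

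**What to change.** In Section 13.7, state that:

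- for PFS, the time-varying Cox model uses only CSF values dated before the PFS event and excludes the sample triggered by progression or stopping therapy;
- for ORR and CBR, the models use only the baseline and cycle 2 day 15-21 samples;
- the progression/off-therapy sample is reported descriptively and in the tumor-CSF-plasma comparisons, and stays in the OS model as a time-varying covariate.

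Because the first scan falls in the same window as the cycle 2 sample, add a sentence saying how a sample is classed when that scan shows progression.

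A landmark at cycle 3 day 1 may be added as a sensitivity analysis, but it should not be the main method. Under the protocol's medians of 3.5 and 2 months, about 24-38% of patients would have progressed by week 6, leaving about 7.6 to 6.2 of 10 (10 × 0.76 and 10 × 0.62).

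The change is to wording only, with the same samples and assays. The cost is that fewer samples enter the exploratory PFS, ORR and CBR models.
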